9.5 Criteria for Study Termination

The study continues until all 40 patients have been treated.

9.6 Missing Values

No imputation for missing values will be utilized.

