In the event of early termination, a visit will be performed whenever possible, including a final blood sample and all end of treatment assessments that should be completed as soon as possible. All patients with at least 1 week of treatment will be

eligible for analysis.

Number of Patients:

A maximum of 40 patients will be enrolled in intervention part of this study and randomized 1:1 into one of the two groups [20 patients per group] using an internet based randomizer software [<https://www.randomizer.org/>]. We may screen up to an extra 10 patients to compensate for possible drop outs, withdraw consent or those who discontinued for any other reason.

We will also recruit up to 10 healthy volunteers to provide a blood sample [1 tube, 5 ml] to serve as a reference arm for the cytokine analysis. This reference group will be seen only once and will not participate in any other study activities.

Consequently, the total number of participants in this study will be n=50.

Inclusion criteria for patients:

1. Have a confirmed diagnosis of relapsing MS defined by the 2010 Revised McDonald Criteria for the Diagnosis of Multiple Sclerosis¹
2. Have a baseline Expanded Disability Status Scale (EDSS) ≤ 7.0
3. Age equal or older than 18 years of age
4. Be able to attend all clinic appointments without interruption
5. Be proficient in English
6. Be willing and able to give written informed consent
7. Negative blood pregnancy test at screening

Exclusion criteria for patients

1. Not meeting all of the above inclusion criteria
2. Pregnancy [current or planned for the near future] or breastfeeding
3. All qualified patients will not be currently or recently [90 days] treated with immunosuppressive therapy [i.e. chemotherapy] or high dose corticosteroids [i.e. 1g of prednisone or greater or equivalent]. Immune-Modulatory therapies are allowed as per standard of care.
4. Ongoing use of antibiotics
5. Presence of a chronic intestinal disease e.g. celiac, mal-absorption, colonic tumor
6. Concomitant inflammatory diseases
7. Standard of care exclusions for MRI scans as per LHSC standards

Healthy controls Selection:

1. Age equal or older than 18
2. Written informed consent
3. Self reportedly “healthy”, in particular not having a history of any disease or

disorder, or any treatment ever for such [ie lupus, cancer, etc], that in the opinion of the PI could be possibly related to changes in the immune system that would alter the results of a cytokine in blood analysis.

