Patients will also undergo a contrast-enhanced brain MRI scan at Robarts Institute in London Ontario. Other baseline assessments (prior to the first dose of therapy) include an EDSS, pregnancy test (if applicable), and physical exam. Blood samples are also taken at this visit in order to establish a baseline for routine chemistry/hematology. After all this assessments FMT will be performed by a trained nurse via a rectal enema

Patients will return to the clinic for visit 4 weeks after the first FMT. Another stool sample to evaluate the microbial before the second FMT will be collected. Also peripheral blood samples for cytokines and blood bacterial DNA analysis. This same routine procedure will be

repeated at month 2, 3, 4 and 5 for the early intervention group and at month 6, 7, 8, 9, 10 and 11 for the late intervention group. Both groups will come to clinic at baseline and month 1 to 12 inclusive, even if they are not receiving FMT. During all visits, a stool sample, a cytokine sample and a blood DNA bacteria sample will be collected. It is worth mentioning that at 6 and 12 months another urine analysis will be done to evaluate gut permeability and MRI study at Robarts Institute, London, Ontario for safety assessment will be performed for both groups.

Another safety assessment in each visit after FMT is to review of any adverse events that may have occurred. All patients receiving at least 1 week of treatment will be eligible for analysis.

Table 1. Early Intervention Group Schedule

[figure not shown]
Study Months	Pre-Visit	Baseline	Month 1	Month 2	Month 3	Month 4	Month 5	Month 6	Month 7	Month 8	Month 9	Month 10	Month 11	Month 12
Visit Duration	1.5hours	1.5hours	1.5hours	1.5hours	1.5hours	1.5hours	1.5hours	45min	45min	45min	45min	45min	45min	45min
Informed Consent Form	X													
Fecal Transplantation		X	X	X	X	X	X							
Height		X												
Weight, Vital Signs		X	X	X	X	X	X	X	X	X	X	X	X	X
Stool Sample		X	X	X	X	X	X	X	X	X	X	X	X	X
Urine: Gut Permeability		X						X						X
Circulating Cytokine Levels and Blood DNA		X	X	X	X	X	X	X	X	X	X	X	X	X
MRI		X						X						X
Routine Hematology and Urinalysis		X	X	X	X	X	X	X	X	X	X	X	X	X
Physical Exam/ EDSS		X	X	X	X	X	X	X	X	X	X	X	X	X

Table 2. Late Intervention Group Schedule

Study Months	Pre-Visit	Baseline	Month 1	Month 2	Month 3	Month 4	Month 5	Month 6	Month 7	Month 8	Month 9	Month 10	Month 11	Month 12

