Successful adherence will be defined as =90% of patients progressing to FMT and all follow-up. Preliminary estimates of non-administration of the trial intervention are needed, along with strategies that maximize exposure to the intervention.

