6.2.3 Peripheral blood cytokines levels

Cytokine levels will be measured as previously described⁷². Peripheral blood will be collected into EDTA blood collection tubes ensuring complete mixing with anticoagulant to avoid clotting. Within 60 minutes of blood collection samples will be spun for 10 minutes at 4500xg. The plasma will be collected and aliquoted into cryovials. All samples will be collected and stored at -80°C before the plasma is measured for 25 immunological cytokines using a luminex-based multiplexed immunoassay. The Human Th17 Magnetic bead panel (HTH17MAG-14K, Millipore) will be used in this study to detect changes in Interleukin 1 β (IL-1 β), IL-2, IL-4, IL-5, IL-6, IL-9, IL-10, IL-12p70, IL-13, IL-15, IL-17A, IL-17E/IL-25, IL-17F, IL-21, IL-22, IL-23, IL-27, IL-28A, IL-31, IL-33, granulocyte macrophage colony stimulating factor (GM-CSF), interferon γ (IFN γ), macrophage inflammatory protein 3 α (MIP-3 α), tumour necrosis factor α (TNF α) and TNF β . Plasma samples will be run in duplicate and assays will be standardized as per product specifications. Plasma cytokine levels in healthy controls will be compared to levels in MS patients at all time points. Moreover, cytokine levels of MS patients at baseline (D0) will be compared to levels at 12 months to determine whether intervention (FMT) had an effect on pro- and anti-inflammatory cytokine levels.

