7.0 ASSESSMENT OF EFFICACY

As this study is an immunological study, the following efficacy outcomes will be evaluated:

- Changes in peripheral blood cytokines within RMS patients between baseline and months 1 to 12 inclusive, for both groups. Luminex kit will be used.
- Changes on microbiome after FMT by analyzing the gut bacterial composition through stool analysis and blood bacteria DNA at baseline, and months 1 to 12 inclusive for both groups.
- Gut permeability through urine analysis at baseline, 6 and 12 months for both groups.

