9.3 Biomarkers

We will analyze mean differences between two independent groups whilst subjecting participants to repeated measures overtime to assess variability between- and within-subjects variable. Therefore, we will use the mixed-design ANOVA model.

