9.7 Evaluable Patients

All patients who received 1 week of study treatment will be included in all analyses and listings.

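### The mixed-design ANOVA in 9.3, run in its conventional form, drops a treated patient for one missed cytokine sample although 9.7 includes that patient; the plan names no form that keeps such patients.

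*Combined protocol and SAP*

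**What the plan says.** Section 9.3 describes a comparison of two independent groups with repeated measures and concludes: "Therefore, we will use the mixed-design ANOVA model". It gives no estimation method, covariance structure or list of visits.

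Section 9.6 is one sentence: "No imputation for missing values will be utilized". Section 9.7 is also one sentence: "All patients who received 1 week of study treatment will be included in all analyses and listings".

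Section 4 fixes the sampling: "During all visits, a stool sample, a cytokine sample and a blood DNA bacteria sample will be collected". With baseline and months 1 to 12, that is 13 cytokine samples per patient. Two sections point to different sets of visits for the analysis. Section 7.0 lists "Changes in peripheral blood cytokines within RMS patients between baseline and months 1 to 12 inclusive, for both groups", while section 6.2.3 says that "cytokine levels of MS patients at baseline (D0) will be compared to levels at 12 months" to judge whether FMT had an effect.

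The plan expects incomplete patients. The synopsis says: "In the event of early termination, a visit will be performed whenever possible, including a final blood sample". Section 5.4 sets the goal: "Successful adherence will be defined as =90% of patients progressing to FMT and all follow-up".

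**The concern.** A conventional between-within ANOVA works on complete rows. With imputation ruled out, a patient with a gap at any analysed visit cannot enter, and the samples that patient did give are discarded. For treated patients this conflicts with section 9.7. It also wastes the final blood sample that the synopsis asks for from patients who stop early.

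Because the plan does not say which form of the model will be used, the handling of partly observed patients in the primary analysis is left to a software default or to a choice made once the data are visible. With 20 patients per group, each lost patient costs precision. If missed visits are related to relapse or adverse events, the remaining complete patients may also be a selected group.

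The point concerns patients covered by 9.7. A late-group patient who leaves before the first FMT at month 6 has had no study treatment and falls outside that section; this is a separate question.

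**Working it through.** The plan states no missing-data rate and no figure for the loss, so there is nothing of its own to reproduce. The inputs are 40 patients, 20 per group (section 4); 13 cytokine samples (sections 4 and 7.0); and the 90% goal (section 5.4).

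**1. Loss at the plan's own goal.** If 90% complete everything, 0.90 × 40 = 36 patients are complete and 4 are not, or 18 complete per group if they split evenly. The standard error relative to 40 complete patients is √(40/36) = 1.054, an increase of 5.4%. If misses were independent across visits, this goal would correspond to 1 − 0.9^(1/13) = 0.81% missing per visit.

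**2. Observed samples discarded, counting only patients within 9.7.** Assume two dropouts per group, each leaving after 1 to 12 samples with equal chance.
- Early group: mean (1 + 2 + … + 12)/12 = 6.5 samples each; 2 × 6.5 = 13.
- Late group: FMT starts at month 6, the seventh sample, so only dropouts with 7 to 12 samples are taken as treated. Expected samples per dropout: (7 + 8 + … + 12)/12 = 57/12 = 4.75; 2 × 4.75 = 9.5.
- Total: 13 + 9.5 = 22.5, so about 22 samples. They come from an expected 2 + 2 × 6/12 = 3 treated patients. The fourth incomplete patient is, on average, outside 9.7.

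**3. Precision recovered by using those samples.** This was calculated by generalised least squares. The model has a common baseline mean and separate visit means per group. The assumed between-patient share of variance is 0.3, 0.5 or 0.7, with first-order autocorrelation of 0.3 within patients. Results are averaged over 300 random dropout patterns. Standard errors are relative to 40 complete patients:

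| Group difference | Complete cases | All observed samples, 9.7 set |
|---|---|---|
| Mean of months 1-6 | 1.054 | 1.018-1.019 |
| Month 12 alone | 1.054 | 1.043-1.049 |

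The months 1-6 mean is a contrast chosen for this check; the plan does not name it. Month 12 gains little because a patient who has left contributes to it only through correlation with earlier samples.

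**4. Dependence on the missing rate and on the visits used.** The expected number lost of 40 is 40 × [1 − (1 − p)^k], for an assumed independent missing rate p per visit and k visits in the model:

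| p | k = 13 | k = 7 (baseline to month 6) | k = 2 (baseline, month 12) |
|---|---|---|---|
| 1% | 4.9 | 2.7 | 0.8 |
| 2% | 9.2 | 5.3 | 1.6 |
| 3% | 13.1 | 7.7 | 2.4 |
| 5% | 19.5 | 12.1 | 3.9 |

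All four rates are worse than the 0.81% implied by the goal. If misses cluster within patients (beta-binomial, correlation 0.05 to 0.4), the 13-visit losses fall to 3.9-1.5, 7.4-3.0, 10.6-4.5 and 16.1-7.2.

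**The case against.** The strongest reply is that the plan contains no contradiction. Nothing in it calls for listwise deletion. A group-by-time model, no imputation and all treated patients included can be satisfied together by fitting the model to all observed samples, and 9.7 can be read as requiring this. That much stands. A reader might infer that 9.3 and 9.6 together prescribe a complete-case analysis, or that the three sections cannot be reconciled. The documents support neither. What they show is that the method as named is conventionally run on complete rows and that no other form is specified.

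A reader might also infer that a quarter or half of the trial will be lost. That needs independent misses of about 2-5% per visit and all 13 visits in the model. At those rates only 77% to 51% of patients would be complete, well below the plan's goal. Section 5.2.1 also requires patients to be able to attend every appointment, which should keep misses low. Under the reading in 6.2.3, baseline against month 12, the same rates lose only 1.6 to 3.9 patients.

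The study is also described as exploratory, with an arbitrarily chosen size (section 9.1). This lowers the stakes but does not settle how the primary outcome will be analysed. Finally, a mixed model does not cure bias if missed visits depend on relapse or adverse events in ways that the observed cytokine values do not capture. That is correct, and it limits what the fix can claim.

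**Conclusion.** The point holds as a gap with a better method readily available. The named ANOVA, run conventionally, would exclude treated patients whom 9.7 includes, and the plan does not say that another form will be used.

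The only size that rests on the documents is modest: a standard error about 5.4% larger if the 90% goal is just met. The recoverable part, from 5.4% to about 1.8-1.9% for months 1-6 and to about 4.3-4.9% for month 12, depends on the assumed variance components, two dropouts per group and a uniform time of leaving. Greater losses are possible but rest on assumed missing rates and on how many visits enter the model, which sections 7.0 and 6.2.3 leave open. The change should be made because it is cheap and fixes the method in advance; the documents do not show a large loss.

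**What to change.** In 9.3, replace the mixed-design ANOVA with a linear mixed model fitted by REML to all observed samples, with group, visit and group-by-visit. Keep baseline as one of the responses, with a common baseline mean for the two randomised groups. Every treated patient with at least one sample is then modelled, and baseline is still adjusted for. Entering baseline as a covariate would instead leave out treated patients with no baseline sample, against 9.7.

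Pre-specify a covariance that allows for stable differences between patients, for example a patient random intercept plus autocorrelated errors; the exact choice is the statistician's. State which visits enter the model, so that 7.0 and 6.2.3 agree. Keep the no-imputation rule in 9.6 and add that patients are not dropped for a missed visit.

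The cost is SAP wording and slightly more analysis work, with no new data. Results will rely on missing-at-random and on the covariance choice, and the gain is small if few samples are missed.

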9.7 Evaluable Patients

All patients who received 1 week of study treatment will be included in all analyses and listings.

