- To evaluate the safety of FMT in MS patients
- To evaluate tolerability of FMT in MS patients

Trial Design:

The proposed randomized, open label, controlled [treatment as usual control group], crossover study will be conducted in 40 patients (n=20 per group) diagnosed with the relapsing forms of multiple sclerosis according to the McDonald 2010 Criteria¹.

Based on the diagnostic criteria patients will be further screened to confirm eligibility and if eligible then consented.

Patients will be randomized 1:1 into two groups. One group will receive FMT, done by rectal enema administered by a RN, at baseline, month 1, month 2, month 3, month 4, and month 5 (early intervention group). The other group will receive treatment as per standard of care (treatment as usual control group) in the beginning of the study. For the last 6 months they will also receive FMT at month 6, month 7, month 8, month 9, month 10, and month 11 (late intervention group).

Clinical visits for both groups will be performed at baseline, and months 1 to 12 inclusive. During these visits a physical exam with vital signs, including a standardized neurological assessment Expanded Disability Status Scale – EDSS) will be done.

Patient's stools will be collected before each FMT procedure in both groups to evaluate gut microbial composition.

Urine will be collected to evaluate gut permeability at baseline, 6 and 12 months for both groups.

Peripheral blood samples also will be collected to evaluate circulating cytokine levels (IL-1 β , IL-2, IL-4, IL-5, IL-6, IL-9, IL-10, IL-12p70, IL-13, IL- 15, IL-17A, IL-17E/IL-25, IL-17F, IL-21, IL-22, IL-23, IL-27, IL-28A, IL-31, IL-33, GM-CSF, IFN γ , MIP-3 α , TNF α and TNF β) at baseline, months 1 to 12 inclusive for both groups.

Peripheral blood samples will also be collected to evaluate blood DNA bacteria at baseline, and months 1 to 12 inclusive for both groups.

Brain MRI with gadolinium [3T MRI machine at Robarts Research Institute] will be performed at baseline, 6 and 12 months for both groups as a safety biomarker [to rule out paradoxical effects; i.e. significant increase in MS activity as defined by Cutter's rule: 5 or more newly enhancing white matter lesions in the brain compared to the previous scan].

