Test product, dose and mode of administration, batch number to be provided by [name] lab at St. Joseph's Health Care, London, ON. For this study, fecal samples from healthy donors will be screened as per Health Canada guidelines. About 50-70g of the fecal sample is blended in 220ml saline in a Stomacher and filtered and transferred to an enema bag for transplantation. From here on this is known as "FMT" or "study medication".

Lot no. XXXXXX

Duration of treatment/study:

FMT rectal enema will be administered as scheduled per group, for up to 6 months.

Criteria for evaluation:

- Circulating cytokines levels (IL-1 β , IL-2, IL-4, IL-5, IL-6, IL-9, IL-10, IL-12p70, IL-13, IL-15, IL-17A, IL-17E/IL-25, IL-17F, IL-21, IL-22, IL-23, IL-27, IL-28A, IL-31, IL-33, GM-CSF, IFN γ , MIP-3 α , TNF α and TNF β).
- Gut microbiome through feces analysis
- Blood DNA bacteria
- Gut permeability through urine analysis
- All adverse events occurring during this study will be recorded. MS clinical functional status will be monitored using EDSS to assess any changes during the treatment period, as well as head MRI as a safety surrogate.

Statistical methods:

Adverse events will be coded using MedDRA dictionary. Incidence of adverse events by the severity, relationship to treatment, and outcome will be provided. Narratives of all serious adverse events and events causing death will be included. Laboratory parameters, vital signs and other safety parameters will be documented with the use of descriptive statistics.

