Fecal microbiota transplantation is the process of **fecal** bacteria transfer from a healthy donor into a recipient. The goal is to restore **colonic microflora** by transplanting healthy bacterial flora (e.g. by **enema, orogastric tube** or by mouth in the form of a capsule containing **freeze-dried** material)¹². For this study we selected the enema that is a lower risk procedure compared to an upper tract endoscopy and more easily accepted for patients than an oral capsule of fecal bacteria. An enema will be done to infuse the study treatment into the **lower bowel** through the **rectum** by a trained nurse.

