6. TREATMENT OF PATIENTS

6.1 Study Drug

Fecal microbiota.

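### The evaluable-patient rule in Section 9.7, read as exposure to FMT, leaves out control patients who leave before month 6 but keeps early-group patients who leave after week 1

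*Combined protocol and SAP*

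**What the plan says.** Three places say who is analysed.

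- Section 9.7 (Evaluable Patients): "All patients who received 1 week of study treatment will be included in all analyses and listings".
- Clinical Study Synopsis, Trial Design: "All patients with at least 1 week of treatment will be" eligible for analysis.
- Section 4 (Study Design): "All patients receiving at least 1 week of treatment will be eligible for analysis".

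No all-randomised, safety or per-protocol set is defined elsewhere.

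The two groups start FMT six months apart. The early group has its first FMT at baseline. For the late group the synopsis says "The other group will receive treatment as per standard of care (treatment as usual control group) in the beginning of the study", and then "For the last 6 months they will also receive FMT at month 6" and monthly to month 11.

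On terms, Section 2.2 says "An enema will be done to infuse the study treatment into the" lower bowel, so there *study treatment* is the FMT material. Section 8.2.1 speaks of the initiation of study treatment, which fits an intervention that the study starts. Section 6.1 names the study drug as "Fecal microbiota", and Section 4.2 gives it for 6 months in each group. The synopsis, however, also uses the bare word *treatment* for the control group's usual care.

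**The concern.** Membership of the only defined set depends on something that happens after randomisation and at a different time in each group. If *study treatment* means FMT, an early-group patient enters the set in the second week, and a control patient must stay about six months to enter it. Months 0 to 6 are the only period in which FMT is compared with no FMT between randomised groups, so the unequal rule falls on the period that matters most for a controlled comparison.

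Because Section 9.7 covers all analyses and listings, it would also remove these control patients from the baseline description (Section 9.2) and from the adverse-event, laboratory and vital-sign summaries (Section 9.4). Safety is a secondary objective, and the control period is its only concurrent reference. The synopsis asks for a final blood sample at early termination; for these patients it would be taken and then belong to no analysis.

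Separately, a threshold of 1 week has no clear meaning for an enema given once a month.

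**Working it through.** **Step 1. What the wording permits.** The plan states no figure to reproduce on this point, so the first check is textual.

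- Both terms mean FMT in all three places: the sentences agree, and the two groups qualify about six months apart.
- Both terms mean the assigned arm, including usual care: the sentences agree, and both groups qualify after 1 week.
- *Study treatment* (Section 9.7) means FMT and *treatment* (synopsis, Section 4) includes usual care: the sentences give different sets.

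Sections 2.2 and 8.2.1 favour FMT for the term used in Section 9.7. Section 6.2.1 points the same way, since it says that the control group receives treatment in the last 6 months. The usual-care reading has its own difficulty: Section 2.6 allows patients who are on no disease-modifying therapy, and it is unclear when such a patient has had 1 week of treatment.

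**Step 2. Inputs for size, on the FMT reading.**

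- 20 patients per group (synopsis; Section 4).
- First FMT at baseline (early) or month 6 (late).
- Leaving probability *q* by month 6, equal in both groups: not in the documents. Two figures give a rough anchor, and both refer to the whole study. The 90% adherence target in Section 5.4 implies 10% over 12 months, or about 5% by month 6 if leaving is uniform. The up to 10 extra patients in the synopsis imply 10/50 = 20%, or about 10% by month 6, and may include screen failures. I add 20% by month 6 as a stress value.
- Leaving time uniform over 26 weeks (assumed).

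**Step 3. Formulas.**

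- Late-group exclusions: 20*q*. Early-group exclusions (leaving in week 1): 20*q*/26.
- Chance of at least one exclusion: late 1 − (1 − *q*)^20; early 1 − (1 − *q*/26)^20.
- Control time lost: 20*q* leavers × 3 months on average = 60*q*. Control time observed: 20(1 − *q*) × 6 + 60*q* = 120 − 60*q*.

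| *q* | Late excluded | Early excluded | At least one, late | At least one, early | Control patient-months lost |
|---|---|---|---|---|---|
| 5% | 1 | 0.04 | 64% | 4% | 3/117 = 2.6% |
| 10% | 2 | 0.08 | 88% | 7% | 6/114 = 5.3% |
| 20% | 4 | 0.15 | 99% | 14% | 12/108 = 11.1% |

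Early-group time lost is negligible: at *q* = 20%, 0.154 patients × half a week is about 0.018 patient-months.

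**Step 4. Cytokines.** Section 9.3 plans a mixed-design ANOVA and Section 9.6 rules out imputation. If the ANOVA uses complete series, every patient who leaves before month 6 drops out in both groups, whatever Section 9.7 says. A simulation agrees. It used months 0 to 6, no FMT effect, within-patient correlation 0.5, leavers' later values shifted by 0.5 or 1 SD of change, *q* from 10% to 30%, and 10,000 replicates per setting. Bias in the month-6 change stayed within 0.006 SD, and the group-by-time type I error was 4.4% to 5.2%. In the baseline-to-month-12 comparison of Section 6.2.3, leavers in both groups lack a month-12 value, so the rule adds no imbalance there either.

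**The case against.** The strongest reply is that this is an undefined term and nothing more. The three sentences share one threshold and can be read alike, the synopsis calls usual care *treatment*, and Section 9.7 says who is included without expressly excluding anyone. A reader might infer that the three sentences contradict each other. The documents do not support that: the sets differ only if the terms are given different meanings. But the reading nearest to the plan's own usage is FMT, no other set would catch the omitted control patients, and a rule that can be read this way should not decide membership in a randomised comparison.

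A second reply is that safety data are protected. In part they are. Section 9.4 promises narratives of all serious events, and Section 8.2.1 defines an adverse event as any undesirable event during trial participation, related to the product or not. So it would be wrong to infer that the definition leaves out control-period events. What remains exposed is the summary and listing of non-serious events, laboratory values and vital signs for control leavers. In addition, Section 4 ties adverse-event review to visits after FMT.

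A third reply is that the numbers are small and the study is exploratory, with a convenience sample (Section 9.1). That is fair: at 5% to 10% leaving, the rule touches one or two patients. It supports a modest rating, not leaving the rule as it is.

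**Conclusion.** The point holds as an unequal, ambiguously worded inclusion rule that is worth correcting before analysis. On the FMT reading, and with equal and uniform leaving of 5% to 20% by month 6, it removes about 1 to 4 of 20 control patients and almost no early-group patients, and takes 2.6% to 11.1% of observed control time out of the safety summaries. If usual care counts as treatment, these figures fall to zero. The leaving rates are assumptions, and the 20% row is a stress value.

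A reader might go further and infer that the cytokine result is biased. That is not shown. Under a complete-case ANOVA the effect is negligible. Bias would need partial series to be used, early leavers kept, late leavers dropped, and leavers' cytokine change to differ from that of stayers. The plan names no such fit. Nor is a planned safety test biased, because Section 9.4 is descriptive and names no comparison of exposed with unexposed time. The firm gain from a correction lies in the control-period safety and baseline summaries, and in removing a selection rule that acts after randomisation.

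**What to change.** Replace the rule in the synopsis, Section 4 and Section 9.7 with one wording.

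- **Efficacy set:** all randomised patients with a baseline cytokine sample, analysed as randomised. How far partial series contribute depends on the model. Under a complete-series ANOVA they would not, and changing the model is a separate decision.
- **Safety and baseline summaries:** all randomised patients, with time before first FMT shown separately from time after it.
- **Sensitivity set, if wanted:** patients with at least one FMT, in place of a 1-week threshold.
- **Adverse-event review:** align Section 4 with the general definition in Section 8.2.1, so that adverse events are reviewed at every scheduled visit in both groups from baseline.
- **Reporting:** give the number of leavers by group and month.

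The cost is a protocol amendment and slightly more analysis work. Both groups already attend every month (Section 4), so no extra visits are needed. The change removes the unequal rule; it does not remove bias if rates of leaving, or reasons for it, differ between the groups.
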